# 3.1.1 Cycles 1-4 and 5-8

- Cycle 1 ONLY: Carfilzomib 20 mg/m² per dose, days 1 and 2; Carfilzomib 36 mg/m² per dose, days 8, 9, 15, and 16
- Cycles 2-8: Carfilzomib 36 mg/m^2 per dose, days 1, 2, 8, 9, 15, and 16
- Cycles 1-8: Lenalidomide 25 mg/day, days 1–21 every 28 days
- Cycles 1-4: Dexamethasone 20 mg/dose, days 1, 2, 8, 9, 15, 16, 22, and 23
- For patients who choose to undergo stem cell harvest, the next cycle may be delayed for up to 5 weeks.
- Cycles 5-8: Dexamethasone 10 mg/dose, days 1, 2, 8, 9, 15, 16, 22 and 23 followed by extended lenalidomide

After receiving first 4 cycles, patients who are considered to be eligible for subsequent high dose therapy/autologous stem cell transplant (ASCT) will be encouraged to undergo autologous stem cell harvesting for potential use in the future. In accord with current clinical standards, the decision whether a given patient is eligible for subsequent high dose therapy/ASCT, or not, will be based on a clinical assessment conducted by the transplant center that evaluates the patient.

[figure not shown]
# 3.1.2 Maintenance and Ongoing Treatment or Follow-Up

After 8 cycles, patients will proceed to extended dosing phase I of lenalidomide (Days 1-21 of 28 day cycle) for 12 cycles. After 12 cycles of extended dosing of lenalidomide, patients who maintain their current clinical response and do not meet criteria of PD as defined in Section 6.3 will have the option to continue lenalidomide as clinically indicated for an additional year on extended dosing phase II.

After 2 years of maintenance, patients will be followed by clinical and laboratory examination every 3-6 months until disease progression requiring treatment. If patients progress, they may be contacted by phone or email to gather survival information. (Note: patients who have not progressed after 2 years of maintenance therapy, but decide to continue lenalidomide maintenance at an outside facility, may also be followed on this protocol as above for long term follow-up at the discretion of the investigator. This follow up will consist of clinic and laboratory examination, however, if the patient is undergoing these investigations at an outside facility, follow-up can be limited to NIH investigator-patient or NIH investigator-outside physician communication of test results.)

[figure not shown]
Of note: On October 19, 2015, the study was closed to accrual for administrative reasons. Eighteen patients had enrolled at that time. Effective with Amendment H (version date 06/12/17), the study status will change to "Open-Recruiting" to allow for enrollment of the remaining 10-12 patients as per the statistical analysis plan of this protocol.

Version Date: 01/01/2024

## 3.2 DRUG ADMINISTRATION

3.2.1 Induction Phase: Cycles 1-8 with 28 day cycles

# 3.2.2 Agents

#### 3.2.2.1 Carfilzomib

- Cycle 1: 20 mg/m^2 IV infusion over 30 minutes on days 1 and 2, then 36 mg/m^2 IV on days 8, 9, 15, and 16
- Cycle 2-8: 36 mg/ m^2 IV infusion over 30 minutes on days 1, 2, 8, 9, 15, and 16
- See Section 14.1.3 for drug formulation and preparation instructions

### 3.2.2.2 Lenalidomide

- Cycle 1-8: 25 mg oral days 1-21 of 28-day cycle
- Lenalidomide capsules should be swallowed whole, and should not be broken, chewed or opened.
- If a dose of lenalidomide is missed, it should be taken as soon as possible on the same day. If it is missed for the entire day, it should not be made up.
- Patients who take more than the prescribed dose of lenalidomide should be instructed to seek emergency medical care if needed and contact study staff immediately.
- Lenalidomide (Revlimid®) will be provided to research subjects for the duration of their participation in this trial at no charge to them or their insurance providers (unless they continue lenalidomide maintenance at an outside facility). Lenalidomide will be provided in accordance with the REMS® program of Celgene/BMS Corporation. Per standard REMS® requirements all physicians who prescribe lenalidomide for research subjects enrolled into this trial, and all research subjects enrolled into this

Version Date: 01/01/2024

trial, must be registered in and must comply with all requirements of the REMS® program. Prescriptions must be filled within 7 days. Only enough lenalidomide for one cycle of therapy will be supplied to the patient each **cycle**.

#### 3.2.2.3 Dexamethasone

• Cycles 1-4: 20 mg oral or IV on days 1, 2, 8, 9, 15, 16, 22, and 23

• Cycles 5-8: 10 mg oral or IV on days 1, 2, 8, 9, 15, 16, 22, and 23

In Cycle 1, the following supportive care measures will be implemented:

- Hydration will be administered prior and subsequent to carfilzomib dosing.
  - Oral hydration: All subjects must be well hydrated (i.e., volume replete). Begin oral hydration equal to approximately 30 mL/kg/day (~6–8 cups of liquid per day), starting 48 hours prior to the planned first dose of carfilzomib.
  - O IV hydration: 500 mL (250 mL before & 250 mL after carfilzomib) OR 1000 mL (500 mL before & after carfilzomib) of normal saline or other appropriate IV fluid formulation must be given before and after each carfilzomib dose during Cycle 1. Total volume will be determined at the discretion of clinician and volume status of patient.
- In subjects considered to be still at risk for TLS at completion of Cycle 1, hydration should be continued into subsequent cycles if clinically indicated.

# 3.2.3 Harvesting Stem Cells

- After receiving first 4 cycles, patients who are considered to be eligible for subsequent high dose therapy/autologous stem cell transplant (ASCT) will be given the option to undergo autologous stem cell harvesting (not as part of this protocol) for potential use in the future.
- Collection and delivery can be conducted at outside institutions. In accord with current clinical standards, the decision whether a given patient is eligible for subsequent high dose therapy/ASCT, or not, will be based on a clinical assessment conducted by the transplant center that evaluates the patient.
- If harvesting and delivery of high dose therapy/autologous stem cell transplant is conducted at NIH Clinical Center, it will be conducted under a separate protocol.
- Transplant eligible patients will be defined as age <75 years with no significant disease co-morbidities and ECOG ≤2.
- For patients who choose to undergo stem cell harvest, next cycle may be delayed for up to 5 weeks.

# 3.2.4 Extended Dosing Phase I: Cycles 9-20

- Patients will go on to receive extended dosing with oral lenalidomide 10 mg/dose, given daily for 21 days of a 28 day cycle, for 12 cycles.
- Lenalidomide ordered in the extended dosing phase of the study will be prescribed by NIH Clinical Center physicians in one month increments for all patients. Upon completion of phone counseling per the REMS® program, the NIH Clinical Center

*Version Date:* 01/01/2024

physician will prescribe a 28 day supply of lenalidomide to be sent to the patient by express delivery.

- For FCBP patients in the extended dosing phase of the study, lenalidomide will be prescribed by NIH Clinical Center physicians in one month increments. FCBP patients will still be required to have medically supervised pregnancy testing as outlined in APPENDIX BAPPENDIX B: Requirements for REMS; and may have the pregnancy test performed by local treating physician. In these cases, the local physician will submit the results to NIH Clinical Center for review. Upon receipt of negative pregnancy test result and completion of phone counseling per the REMS® program, NIH Clinical physician will prescribe a 28-day supply of lenalidomide to be sent to the patient by express delivery.
- 3.2.5 Extended Dosing Phase II (optional): Cycles 21through 32 (effective with Amendment C version date 07/11/2013):
  - After 12 cycles of extended dosing of lenalidomids (phase I), patients who maintain their current clinical response and do not meet criteria of PD as defined in Section 6.2 will have the option to continue lenalidomide 10 mg/dose as clinically indicated for one additional year. For those patients who are ready to begin extended dosing phase II, treatment may be delayed until amendment C (version date 07/11/2013) is approved by the IRB.
  - Lenalidomide will be ordered in extended dosing phase II will be prescribed by NIH
    Clinical Center physicians in one month increments for all patients. Upon completion
    of phone counseling per the REMS® program, the NIH Clinical Center physician will
    prescribe a 28 day supply of lenalidomide to be sent to the patient by express
    delivery.
  - For FCBP patients in the extended dosing phase of the study, lenalidomide will be prescribed by NIH Clinical Center physicians in one month increments. FCBP patients will still be required to have medically supervised pregnancy testing as outlined in **APPENDIX B**; and may have the pregnancy test performed by local treating physician. In these cases, the local physician will submit the results to NIH Clinical Center for review. Upon receipt of negative pregnancy test result and completion of phone counseling per the REMS® program, NIH Clinical physician will prescribe a 28 day supply of lenalidomide to be sent to the patient by express delivery.
  - The duration for extended dosing was determined based on the study design from the Phase III trial Quiredex trial of lenalidomide/dexamethasone followed by lenalidomide maintenance vs. observation in high-risk SMM patients conducted by the Spanish PETHEMA study group. In this study, the treatment arm received 9 cycles of induction therapy with lenalidomide and dexamethasone followed by lenalidomide maintenance. In August of 2011, the Quiredex protocol was amended to stop lenalidomide maintenance treatment after 2 years. In addition, the three largest randomized phase III trials investigating lenalidomide maintenance were published in 2012 with median follow-up periods ranging from 30 months to 45 months. Two out of three of these studies continue lenalidomide maintenance until progression with no planned end date for lenalidomide maintenance.

Version Date: 01/01/2024

#### 3.3 DOSE MODIFICATIONS

NOTE: If patients require lenalidomide dose reductions and experience delays in drug administration (e.g., due to pharmacy not having the correct dosage form and/or time required to get the correct/adjusted dose supply to the patient), these administrative delays will not be considered a reportable protocol deviation. Furthermore, appointments and treatments missed by patients due to logistical reasons including weather and transportation problems will not be considered a reportable protocol deviation. Patients may miss up to 15% of lenalidomide doses. All efforts will be made to attaining and delivering medications to the patient expeditiously.

3.3.1 Dose Reductions: Induction Phase

	Lanalidamida	Carfilzamih	Dexamethasone	
	Lenalidomide	Carfilzomib	Cycles 1-4	Cycles 5-8
Baseline dose	25 mg daily on Days 1-21 of 28 day cycle	$36 \text{ mg/m}^2$	20 mg	10 mg
One level dose reduction	20 mg daily on Days 1-21 of 28 day cycle	27 mg/m 	10 mg	4 mg
Two level dose reduction	15 mg daily on Days 1-21 of 28 day cycle	20 mg/m 	4 mg	0 mg
Three level dose reduction	10 mg daily on Days 1-21 of 28 day cycle		0 mg	
Four level dose reduction	5 mg daily on Days 1-21 of 28 day cycle			

- 3.3.1.1 Lenalidomide and Carfilzomib dosages are not modified in concert; i.e., lenalidomide and carfilzomib dosage reductions are implemented separately. If more than 2 dose reductions are required with Carfilzomib, study treatment will be discontinued and the patient will go off therapy.
- 3.3.1.2 If there is no resolution of toxicity after 2 weeks of withholding treatment or up to 3 weeks for infection related treatment, the subject will go off therapy
- 3.3.2 Hematologic Toxicity: Induction Phase
- 3.3.2.1 Due to the nature of the disease originating in the bone marrow, events occurring within the first two cycles of treatment and deemed to be due to disease burden will be exempt from dose reductions at the discretion of the investigator.
- 3.3.2.2 On day 1 of each new cycle (or day 1 of every third cycle during extension phase), patients must meet the following criteria or dose modify based on dose reductions in table 3.3.1:
  - ANC  $> 1.0 \times 10^9 / L$
  - Platelet count  $\geq$  75 x 10^9/L during cycles 1-8; Platelet count  $\geq$ 50 x 10^9/L during cycles 9 and beyond

If these conditions are not met on Day 1 of a new cycle, a new cycle of treatment will not be initiated until the toxicity has resolved. If there is no resolution after 2 weeks of withholding treatment or up to 3 weeks for infection related treatment, the subject will go off therapy.

*Version Date:* 01/01/2024

If the investigator chooses to dose reduce according to table 3.3.1, the investigator will determine which drug will be modified based on side effect profile and clinical judgment.

3.3.2.3 If a patient develops thrombocytopenia or neutropenia during the cycle, then the following actions would take place (see Thrombocytopenia/Neutropenia table below).

Thrombocytopenia	Lenalidomide	Carfilzomib
Fall to < 25 x 10  /L	Fall to < 25 x 10  /L Hold both Lenalidomide and Carfilzomib, follow CBC weekl Hold prophylactic anti-coagulation.	
Return to $\geq 25 \times 10^9/L$	Resume lenalidomide at next dose reduction	Resume carfilzomib at full dose*
Subsequent fall to < 25 x 10  /L	Hold both Lenalidomide and Carfilzomib, follow CBC weekly. Hold prophylactic anti-coagulation.	
Return to ≥ 25 x 10  /L	Resume lenalidomide at next dose level reduction  Resume carfilzomib at full dose	

\*Carfilzomib may be dose reduced at the clinical discretion of investigator

Neutropenia (Absolute Neutrophil Count)	Lenalidomide	Carfilzomib
Falls to $< 0.5 \times 10^9/L$ or to $< 1.0 \times 10^9/L$ with fever		filzomib. Add filgrastim if Grade 3 are of 38.3°C or sustained temperature de 4. Follow CBC weekly
Returns to $\geq 1.0 \times 10^9/L$	Resume Lenalidomide at next dose reduction.	Resume Carfilzomib at full dose*
Subsequent drop to $< 0.5 \text{ x}$ $10^9/\text{L}$ or to $< 1.0 \text{ x}$ $10^9/\text{L}$ with fever		
Returns to $\geq 1.0 \times 10^9/L$	Resume Lenalidomide at next dose reduction.	Resume Carfilzomib at full dose*

\*Carfilzomib may be dose reduced at the clinical discretion of investigator.

- 3.3.3 Non-Hematologic Toxicity: Induction Phase
- 3.3.3.1 Toxicity ≥ grade 3 will require appropriate study drug to be held until resolved to ≤ Grade 1 unless specified below. Investigator will determine which drug will be held based on side effect profile and clinical judgment.
- 3.3.3.2 Once toxicity has resolved ≤ grade 1, subsequent doses will be reduced at next dose level (according to table in section 3.3.1) if the adverse event was deemed to be treatment related by the PI. If the adverse event was deemed to be unrelated to treatment, the patient may continue the full dose.
- 3.3.3.3 Readily reversible electrolyte and metabolic abnormalities, infections or diarrhea controlled by appropriate therapy are exempt.
- 3.3.3.4 Patients with Grade 3 or higher peripheral neuropathy, Grade 3 or higher non-blistering rash or blistering rash of any grade, grade 3 or higher hypersensitivity reactions will be removed from protocol therapy.

Lenalidomide Toxicities	Dosing Modifications
Blistering Rash (Any Grade)	Discontinue lenalidomide and remove patient from therapy
Venous thrombosis/ embolism	Hold lenalidomide and start therapeutic anticoagulation. Restart lenalidomide at investigator's discretion at current dose level.
Renal Dysfunction CrCl based on Cockcroft-Gault. (Alternatively, MDRD or CKD- epi formulas may be used to estimate eGFR as more accurate indictors of renal dysfunction than	
 
CrCl 31-50 ml/min – Dose reduce lenalidomide to 10 mg daily from Days 1-21
 
CrCl ≤30 mL/min (not requiring dialysis) – Dose reduce Lenalidomide to 15 mg every 48 hours
 
CrCl ≤30 mL/min (requiring dialysis) – Decrease
 
Lenalidomide to 5 mg daily and on dialysis days give
 

indictors of renal dysfunction than CrCl in discrepant cases)	Lenalidomide to 5 mg daily and on dialysis days give lenalidomide dose after dialysis.

Carfilzomib Toxicities	Dosing Modifications
Allergic Reaction/Hypersensitivity	Grade 2: Hold carfilzomib until ≤ Grade 1 and resume at full carfilzomib dose
Tumor Lysis Syndrome (≥ 3 of the following: ≥50% increase in creatinine, uric acid, or phosphate; ≥30% increase in potassium; ≥20% decrease in calcium; or 2-fold increase in LDH	Hold carfilzomib until all abnormalities in serum chemistries have resolved. Resume at full dose
Herpes zoster or simplex of any grade	Hold carfilzomib until lesions are dry. Resume at full dose
Neuropathy	Grade 2 treatment emergent neuropathy with pain: Hold carfilzomib until resolved to $\leq$ Gr 1 without pain. Then restart at next dose level reduction.
Congestive Heart Failure	Any subject with symptoms of congestive heart failure, whether or not drug related, must have the dose held until resolution or return to baseline. After which, treatment may continue at reduced dose or patient may be withdrawn from therapy.
Renal Toxicity: Serum creatinine ≥ 2 × baseline, or Creatinine clearance less than 15 mL/min, or creatinine clearance decreases to less than or equal to 50% of baseline, or need for hemodialysis	Withhold dose and continue monitoring renal function (serum creatinine or creatinine clearance).  If attributable to carfilzomib, resume when renal function has recovered to within 25% of baseline; start at 1 dose level reduction. If not attributable to carfilzomib, dosing may be resumed at the discretion of the physician. For patients on hemodialysis receiving carfilzomib, the dose is to be administered after the hemodialysis procedure.
If Posterior Reversible Encephalopathy Syndrome (PRES) is suspected	If PRES is suspected, hold carfilzomib. Consider evaluation with neuroradiological imaging, specifically MRI, for onset of visual or neurological symptoms suggestive of PRES. If PRES is confirmed, permanently discontinue carfilzomib. If the diagnosis of PRES is excluded, carfilzomib administration may resume at same dose, if clinically appropriate.

Version Date: 01/01/2024

Carfilzomib Toxicities	Dosing Modifications
If thrombotic microangiopathy (TTP/HUS) is suspected	Hold carfilzomib and manage per standard of care including plasma exchange as clinically appropriate. If TMA is confirmed and related to carfilzomib, permanently discontinue carfilzomib. If the diagnosis is excluded, carfilzomib can be restarted at the previous dose. If the condition recurs, permanently discontinue carfilzomib.
Hepatic Impairment:	
Mild to moderate liver dysfunction: defined as 2 consecutive values, at least 28 days apart, of: (1) total bilirubin (> 33% direct) > 1x ULN to < 3x ULN OR (2) an elevation of AST and/or ALT with normal bilirubin Grade 3 elevation in ALT and/or AST (> 5x ULN)	25% dose reduction. Dose may be re-escalated if liver function tests return to normal and drug-induced hepatotoxicity is excluded.  Hold carfilzomib until resolution to baseline.  Monitor any abnormality weekly. Resume carfilzomib with a 25% dose reduction if drug-induced hepatotoxicity is excluded.
Grade 3 elevation in total bilirubin	Hold carfilzomib until resolution to baseline. Monitor total bilirubin and direct bilirubin weekly.  Upon resolution of total bilirubin to normal, resume carfilzomib dosing with a 25% dose reduction if druginduced hepatotoxicity is excluded.
Drug-induced hepatotoxicity (attributable to carfilzomib)	Discontinue carfilzomib
Thrombotic Microangiopathy (TMA)	If the diagnosis is suspected, hold carfilzomib and manage per standard of care including plasma exchange as clinically appropriate. If TMA is confirmed, permanently discontinue carfilzomib. If the diagnosis is excluded, carfilzomib can be restarted.

3.3.4 Dose Reductions: Extended Dosing Phases I and II

	Lenalidomide
Baseline dose	10 mg daily on Days 1-21 of 28 day cycle
One level dose reduction	5 mg daily on Days 1-21 of 28 day cycle

# 3.3.5 Hematologic Toxicity: Extended Dosing Phases I and II

- 3.3.5.1 On day 1 (or within 7 days prior to day 1) of every third cycle during extension phase, patients must meet the following criteria or dose modify based on dose reductions in table 3.3.4:
  - ANC  $\geq 1.0 \times 10^9 / L$

Version Date: 01/01/2024

• Platelet count  $>50 \times 10^9$ /L during cycles 9 and beyond

If these conditions are not met on Day 1 of every third cycle, treatment will not be initiated until the toxicity has resolved or returned to baseline. If there is no resolution after 2 weeks of withholding treatment or up to 3 weeks for infection related treatment, the subject will go off therapy.

3.3.5.2 If a patient develops thrombocytopenia or neutropenia during the cycle, then the following actions would take place (see Thrombocytopenia/Neutropenia table below).

Thrombocytopenia	Lenalidomide				
Fall to < 25 x 10  /L	Hold Lenalidomide, follow CBC weekly. Hold prophylactic anti-coagulation.				
Return to $\geq 25 \times 10^9/L$	Resume lenalidomide at next dose reduction if deemed drug related				
Subsequent fall to < 25 x 10  /L	Hold Lenalidomide. Hold prophylactic anti-coagulation				
Return to $\geq 25 \times 10^9/L$	Patient will go off therapy if deemed drug related				

Neutropenia (Absolute Neutrophil Count)	Lenalidomide			
Falls to < 0.5 x 10  /L or to < 1.0 x 109/L with fever	Hold Lenalidomide. Add filgrastim if Grade 3 with fever (single temperature of 38.30 or sustained temperature of 380 for > 1 hour) or Grade 4. Follow CBC weekly			
Returns to $\geq 1.0 \times 10^9/L$	Resume Lenalidomide at next dose reduction.			
Subsequent drop to $< 0.5 \times 10^9/L$ or to $< 1.0 \times 109/L$ with fever	Hold Lenalidomide. Add filgrastim if Grade 3 with fever or Grade 4. Follow CBC weekly			
Returns to $\geq 1.0 \times 10^9/L$	Patient will go off therapy if deemed drug related			

- 3.3.6 Non-Hematologic Toxicity- Extended Dosing Phase
- 3.3.6.1 Toxicity ≥ grade 3 will require study drug to be held until resolved to ≤ Grade 1 or baseline unless specified below.
- 3.3.6.2 Once toxicity has resolved ≤ grade 1 or baseline, subsequent doses will be reduced at next dose level (according to table in Section 3.3.4) if the adverse event was deemed to be treatment related by the PI. If the adverse event was deemed to be unrelated to treatment, the patient may continue the full dose. In the case of renally adjusted doses, dosing modifications are made according to table below.
- 3.3.6.3 Readily reversible electrolyte and metabolic abnormalities or infections controlled by appropriate therapy are exempt.

Version Date: 01/01/2024

Common Lenalidomide Toxicities	Dosing Modifications				
Non-Blistering Rash	
 
If Grade 3, hold lenalidomide dose and restart at next dose reduction once rash improves to ≤ Grade 1
 
If Grade 4, discontinue lenalidomide and remove patient from therapy
 
				
Blistering Rash (Any Grade)	Discontinue lenalidomide and remove patient from therapy				
Venous thrombosis/embolism	Hold lenalidomide and start therapeutic anticoagulation. Restart lenalidomide at investigator's discretion at current dose level.				
Renal Dysfunction: CrCl based on Cockcroft-Gault. (NOTE: Alternatively, MDRD or CKD-epi formulas may be used to estimate eGFR as more accurate indictors of renal dysfunction than CrCl in discrepant cases.)	
 
CrCl 31-50 ml/min – Dose reduce lenalidomide to 10 mg daily from Days 1-21
 
CrCl ≤30 mL/min (not requiring dialysis) – Dose reduce Lenalidomide to 15 mg every 48 hours and see carfilzomib dosing below.
 
CrCl ≤30 mL/min (requiring dialysis) – Decrease Lenalidomide to 5 mg daily and on dialysis days dose lenalidomide after dialysis.
 
				

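### The extended-dosing renal row in 3.3.6 repeats doses written for a 25 mg start, so against a 10 mg full dose it cuts nothing at CrCl 31–50 and at most 21% at CrCl ≤30 without dialysis

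*Combined protocol and SAP*

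**What the plan says.** The protocol has two treatment phases with different lenalidomide doses.

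- **Induction.** Section 3.2.1 defines it as "Induction Phase: Cycles 1-8 with 28 day cycles". Full-dose lenalidomide is 25 mg on days 1–21 (3.3.1), given with carfilzomib and dexamethasone.
- **Extended dosing.** Section 3.1.2 says "After 8 cycles, patients will proceed to extended dosing phase I of lenalidomide". Section 3.2.4 gives the dose as "extended dosing with oral lenalidomide 10 mg/dose, given daily for 21 days of a 28 day cycle". The reduction table in 3.3.4 lists "10 mg daily on Days 1-21 of 28 day cycle" as baseline and one reduced level, "5 mg daily on Days 1-21 of 28 day cycle".

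Each phase has a renal row among its lenalidomide toxicities, in 3.3.3 for induction and in 3.3.6 for extended dosing. The doses are the same in both:

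- At CrCl 31–50 the 3.3.6 row reads "CrCl 31-50 ml/min – Dose reduce lenalidomide to 10 mg daily from Days 1-21".
- At CrCl ≤30 without dialysis it reads "Dose reduce Lenalidomide to 15 mg every 48 hours and see carfilzomib dosing below". The induction line has the same dose but no carfilzomib pointer.
- At CrCl ≤30 with dialysis, both rows set 5 mg daily, taken after dialysis on dialysis days.

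Section 3.3.6.2 sends renal adjustments to this row and not to the levels in 3.3.4: "In the case of renally adjusted doses, dosing modifications are made according to table below".

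**The concern.** A renal row should lower the dose when clearance falls. The induction row does so, because it starts from 25 mg. The same doses placed in a 10 mg phase no longer do what their verb says: one line restates the full dose, and another sets a single dose larger than the full dose.

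The carfilzomib pointer suggests a carry-over and not a deliberate choice. Extended dosing is lenalidomide alone, and no carfilzomib table follows in 3.3.6. No reason for these doses is given anywhere in the document.

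What is at stake is a written safety rule covering cycles 9–32, up to 24 of 32 cycles. Entry criteria do not make the row unreachable. Under 2.1.1.5, clearance of at least 50 ml/min is required only when creatinine exceeds 1.5 × ULN, and renal function can decline on treatment. Routine labs, which include an eGFR, recur every third cycle in this phase (3.3.7.2; Study Calendar, footnote a). The primary endpoint and the sample size are not affected.

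**Working it through.** The plan states no per-cycle totals, so there is no figure to reproduce. The check is: cycle total = mg per dose × number of doses in a 28-day cycle.

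**Inputs.** Full and reduced doses come from 3.3.1, 3.2.4 and 3.3.4; renal doses come from 3.3.3 and 3.3.6. The every-48-hours and dialysis lines give no dosing days, so each is counted both ways.

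**Dose counts for every 48 hours.**
- Days 1, 3, …, 21: 11 doses, 11 × 15 = 165 mg.
- Days 1, 3, …, 27: 14 doses, 14 × 15 = 210 mg.

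**Induction (full dose 25 × 21 = 525 mg).**
- CrCl 31–50: 10 × 21 = 210 mg; 210/525 = 0.40, so 60% lower.
- CrCl ≤30, no dialysis: 165/525 = 0.31, so 69% lower; or 210/525 = 0.40, so 60% lower.

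**Extended dosing (full dose 10 × 21 = 210 mg).**

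| Situation | mg per cycle | Change from full |
|---|---|---|
| CrCl 31–50 | 10 × 21 = 210 | 0% |
| CrCl ≤30, no dialysis, days 1–21 | 165 | 165/210 = 0.786, 21% lower |
| CrCl ≤30, no dialysis, 28 days | 210 | 0% |
| CrCl ≤30, dialysis, days 1–21 | 5 × 21 = 105 | 50% lower |
| CrCl ≤30, dialysis, 28 days | 5 × 28 = 140 | 33% lower |
| One-level reduction in 3.3.4 | 5 × 21 = 105 | 50% lower |

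**Per-dose and average comparison at CrCl ≤30 without dialysis.** A 15 mg dose is 15/10 = 1.5 times the full single dose. The average is 15/2 = 7.5 mg/day, below the 10 mg/day of a full dosing day. Spread over 28 days the full schedule is also 210/28 = 7.5 mg/day, which is why 28-day dosing gives the same total.

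**Comparison within the phase.** The non-dialysis line gives 165 − 105 = 60 mg to 210 − 105 = 105 mg more per cycle than the one-level reduction used after other related grade 3 non-hematologic toxicity.

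**Phase length.** 32 − 8 = 24 cycles; 24/32 = 75%.

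**The case against.** The strongest reply has four parts.

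1. **The row sets absolute doses by clearance band, not percentages.** If 10 mg is acceptable at CrCl 31–50 in induction, a patient already on 10 mg needs no change. This stands: read as a ceiling, that line is redundant and harmless.
2. **15 mg every 48 hours averages less per day than 10 mg daily, and the phase runs on a 21-day schedule, so 165 mg is the natural total.** This stands in part. A reader might infer that the row raises total exposure. It does not: neither count exceeds 210 mg. But the dosing days are not written, and even 165 mg is well above the phase's reduced level. The same omission in the induction row matters less, because either count there is a cut of at least 60%.
3. **An instruction to reduce cannot raise a dose.** A reader might infer that a patient already on 5 mg would be moved up to 10 mg. The verb in the row is against that, so the text does not support it. A short cap would still remove the doubt.
4. **Nobody can now be affected.** The Study Calendar (footnote g) records that all participants had completed cycle 32 by February 2023, and 8.5 and 11.1 say the manufacturer agreements are no longer active. This stands, and it limits the practical value of the point.

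It cannot be said that 3.3.4 corrects the row, because 3.3.6.2 directs renal adjustments to the row itself. Nor does the general hold in 3.3.6.1 settle it: that rule gives way to anything specified below it, and the row specifies doses.

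**Conclusion.** The renal row in 3.3.6 does not fit the phase it governs. The CrCl 31–50 line produces no reduction. The CrCl ≤30 line for patients not on dialysis produces a 21% reduction or none, depending on unstated dosing days, where the phase's ordinary step down is 50%. The dialysis line is a real reduction of 33% to 50%. The carfilzomib pointer has no target.

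This is a correction to a safety instruction, modest in consequence. It rests on the 10 mg dose in 3.2.4 and 3.3.4 being the intended full dose for cycles 9–32. That the row was copied from induction text is an inference from the matching doses and the stray pointer; the documents do not say so.

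Two things should not be concluded. The documents do not show that any patient had CrCl ≤50 in cycles 9–32, so no one can be said to have been dosed wrongly. They also do not give the right renal doses for a 10 mg start, so the size of any clinical error cannot be stated.

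**What to change.** **If the protocol is reused:**
- Rewrite the 3.3.6 renal row against the 10 mg dose. The 5 mg level in 3.3.4 is available, and 5 mg capsules are supplied (14.2.3). The sponsor should confirm the values as a clinical decision.
- If 10 mg is intended at CrCl 31–50, say there is no change from 10 mg.
- Add a cap: the stated dose, or the current dose if lower.
- State the dosing days for any every-48-hours line.
- Delete the carfilzomib pointer.

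**For this trial:** if any patient had CrCl ≤50 in cycles 9–32, state the dose given in the safety report. Otherwise nothing changes.

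**Cost:** a few lines of text on reuse, and at most one sentence here from data already collected. The downside on reuse is that some patients with CrCl ≤50 would receive less lenalidomide than the present row allows.
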